#### **Data collection:**

Demographic and clinical data set: We collect demographic data including age, gender, race/ethnicity, primary clinical diagnoses for SNF stay with specific focus on dementia subtype, most recent orthopedic surgery (<3 months) or reason for hospitalization, chronic medical conditions (top 3), and baseline medications (number of medications). Beyond the data collected from the video, data specific to the falls is collected either by direct extraction from the platform or from incident reports kept by facilities as (State regulations require facility track and file incident reports for all known falls). For the control population, the time of unwitnessed falls is unknown, but the number of falls and ER visits is collected from the existing facility incident reports. For the population equipped with SafelyYou Guardian, we will have direct access to the time of the fall, the time it took the HIL to verify the fall and call the facility, and the time on the ground. Note that for the residents with SafelyYou Guardian, we expect these values to be in increments of minutes.

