## **AIMS & HYPOTHESES FOR RANDOMIZED, WAITLIST-CONTROL STUDY.**

**Aim #1. To assess whether SafelyYou Guardian + HIL will lower fall rates.** Hypothesis 1. Compared to standard-of-care (waitlist control group), SafelyYou Guardian will reduce fall rates in study participant over the study period of 6 months.

**Aim #2. To assess how use of the SafelyYou Guardian affects time spent on the ground after a fall.** Longer time to fall discovery is associated with higher human suffering and often leads to higher medical morbidity/mortality. Hypothesis 2: SafelyYou Guardian + HIL will reduce time to fall discovery (time from fall to staff notification) to under 5 minutes and reduce time spent on the ground to under 15 minutes. Since there is no way to measure control participants time spend on the ground, the aim will not have a comparison but will be descriptive.

**Aim #3. To assess whether SafelyYou Guardian will lead to improvement in hard clinical outcomes.** Hypothesis 3: SafelyYou Guardian participants will lower ED visits and hospitalizations when compared to control. This reduction in ED and hospitalization will correlate with reduced fall rates (aim #1) and reduced time spent on the ground (aim #2). We will review the strength of the association with aim #1 and #2 outcomes.

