For aim #3, we will ascertain the occurrence of fall in the intervention group by doing follow-up case review of each detected fall. For the control group, we perform biweekly check with facility staff and family regarding knowledge and documentation of any falls. For falls in both the intervention and control group, we will additional collected data regarding occurrence of ED visit and hospitalization days. We will also include occurrence (or absence) of any operations, intensive care unit stays, and other medical procedures. We will also collect mortality data.

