#### Clinical outcomes.

For Aim #1, the primary outcomes are the number of falls detected by facilities using the adverse incident reporting system as per routine facility protocol. While use of video detected falls will be used in the intervention group to assist with prevention of future falls, we will not use this as the actual outcome measure: is not the standard-of-care, and the control group will not have video recorded outcomes. There is a bias for detecting falls using video since existing fall reporting systems do not capture falls which staff do not know about (e.g., when a resident is able to get back in bed after a fall). Staff-detected falls which automatically trigger adverse incident reporting is the “real-world” outcome measure and current stand-of-care. Thus, outcomes will differ by facility (each facility has different adverse incident reporting operations and implementation, hence the randomization at each facility will adjust for such variables).

Aim #2 will be a naturalistic observation of SafelyYou Guardian with HIL for 6 months. Specifically, for all the facilities, the use of the SafelyYou Guardian enables direct notification of falls to front-line staff in the facilities, by intervention of the HIL. We can directly measure time on the ground for the residents as follows: (1) The time of the fall is recorded by

SafelyYou Guardian (which detected it); (2) The time of intervention of the front-line staff is logged by the staff after finding the residents on the ground. This means that for the population with treatment, we can directly measure the time of fall discovery (successful call leading to front line staff intervention), and time on the ground (since time of the intervention is logged by the facility). This is because time on the ground for monitored residents can be measured precisely by video recording. Reduction of the time on the ground can be computed given the difference between the two.

Aim #3 will include number of ER visits and number of hospitalizations. We will obtain information about resident demographics, medical comorbidities, emergency room visits, and hospitalization data by asking the study participant legal representatives. In addition, we will have participant / participant Durable Power of Attorney complete HIPAA consent forms for release of medical records when indicated if the details of data are not available.

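### Three sections give conflicting routes for finding Aim 3 ED visits and hospitalisations, and two of them leave the Hypothesis 3 comparison open to differential ascertainment

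*Combined protocol and SAP*

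**What the plan says.** Hypothesis 3 (Aims & Hypotheses) is a between-arm claim: "SafelyYou Guardian participants will lower ED visits and hospitalizations when compared to control". Three sections of the combined protocol and SAP then describe how the events are found.

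- **Design, Aim #3 paragraph.** "we will ascertain the occurrence of fall in the intervention group by doing follow-up case review of each detected fall". The next sentence reads "For the control group, we perform biweekly check with facility staff and family regarding knowledge and documentation of any falls". The outcome data follow from those falls: "For falls in both the intervention and control group, we will additional collected data regarding occurrence of ED visit and hospitalization days".
- **Data collection.** In general, "data specific to the falls is collected either by direct extraction from the platform or from incident reports kept by facilities". For controls, unwitnessed fall times are not known, "but the number of falls and ER visits is collected from the existing facility incident reports". The sentence on residents with the system lists fall and response times and names no source for their ER visits.
- **Clinical outcomes, Aim #3 paragraph.** The outcomes are numbers of ER visits and hospitalisations, obtained "by asking the study participant legal representatives", with released medical records as a back-up when details are lacking. No arm distinction is made and no contact interval is given.

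The Aim #1 paragraph of Clinical outcomes recognises that video finds falls that routine reporting misses, and for that reason counts only incident-reported falls in both arms. No matching rule is stated for Aim 3.

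**The concern.** In a randomised comparison, outcome events should be looked for with the same effort in each arm. Randomising within facility balances differences between facilities in reporting practice. It does not balance a difference in method that is tied to the arm itself.

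Aim 3 carries the trial's claim about hard clinical outcomes. If one arm's visits are found more completely, the estimated ratio mixes the effect of the system with the completeness of counting. That could create a benefit, hide one or suggest harm. The sections also differ on which events belong to the endpoint, so two analysts could follow the document faithfully and count different visits.

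**Working it through.** The documents give no ED or hospitalisation rate, no target effect and no power for Aim 3, so there is no planned figure to reproduce. The check is a comparison of the sections, followed by an illustration on assumed values.

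**1. The routes side by side**

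| Section | Intervention arm | Control arm | Visit without a fall |
|---|---|---|---|
| Design | Case review of each detected fall, then ED and hospital data for that fall | Biweekly check with staff and family for falls, then ED and hospital data for that fall | Not collected in either arm |
| Data collection | ER source not named | Facility incident reports (ER visits; hospitalisations not mentioned) | Not stated; incident reports are described as filed for known falls |
| Clinical outcomes | Legal representatives, then records | Legal representatives, then records | Counted in both arms, since no restriction to falls is stated |

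No section says which source prevails, how often representatives are asked, or how disagreement between sources is settled. The form of the endpoint also varies: occurrence of ED visits and days in hospital (Design), numbers of events (Clinical outcomes), and a binary variable (Data analysis).

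**2. Which visits can be counted differently**

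Under Design, a visit after a fall that both routes would find is treated alike in the two arms. A visit with no fall is collected in neither. The exposed group is visits after a fall that one route would find and the other would miss. The documents suggest a mechanism in each direction.

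- *More capture in the intervention arm.* Clinical outcomes says video finds falls that staff do not know about. Each such fall could prompt a case review.
- *Less capture in the intervention arm.* Cameras are in the bedroom only (Risk/Benefit Assessment), and 5-10% of Phase I falls occurred in the bathroom (Privacy and security safeguards). Suppose that detected means camera-detected, that the control check finds every fall, that ED visits are proportional to falls, and that nothing else differs. The capture ratio is then between 1 - 0.10 = 0.90 and 1 - 0.05 = 0.95.

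**3. Effect on the rate ratio (capture ratios assumed)**

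Observed ratio = true ratio × (capture in intervention / capture in control).

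| Capture ratio | True 1.00 appears as | True 0.70 appears as |
|---|---|---|
| 0.8 | 0.80 | 0.56 |
| 0.9 | 0.90 | 0.63 |
| 1 | 1.00 | 0.70 |
| 1.11 (= 1/0.9) | 1.11 | 0.78 |
| 1.25 (= 1/0.8) | 1.25 | 0.875 |

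**4. Effect on the false-positive probability (illustrative)**

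Inputs from Data analysis: 230 per arm, 0.49 falls per month, 6 months, giving 0.49 × 6 = 2.94 falls per resident. Assumed: 10% to 30% of falls lead to an ED visit, no dropout, two-sided 5% Wald test on the log rate ratio. Expected visits per arm, E, run from 230 × 2.94 × 0.10 = 67.6 to 230 × 2.94 × 0.30 = 202.9.

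With no true effect and capture ratio r, SE = √[φ(1/E + 1/(rE))], where φ = 1 is Poisson and φ = 2 doubles the variance. The rejection probability is Φ(d - 1.96) + Φ(-d - 1.96), with d = |ln r| / SE.

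For r = 0.9, E = 67.6 and φ = 1: SE = √(0.01479 + 0.01643) = 0.177, d = 0.105/0.177 = 0.60, and the probability is 0.086 + 0.005, about 0.09.

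| r | φ = 1, E from 67.6 to 202.9 | φ = 2, E from 67.6 to 202.9 |
|---|---|---|
| 0.9 | 9% to 18% | 7% to 11% |
| 0.8 | 23% to 56% | 14% to 32% |

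With equal capture (r = 1) it stays at the nominal 5%.

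**The case against.** The strongest reply is that Clinical outcomes is where the Aim 3 outcomes are defined, and its route is the same in both arms. If that route governs the endpoint, the arm-specific steps in Design serve only to describe falls, and the asymmetry disappears. This stands as a possible reading. But the section does not say that it overrides Design or Data collection, and Design is explicit that ED and hospital data are collected for the falls it has just described.

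Second, an ED transfer is an event that staff probably know about in either arm. The document's own example of a missed fall is a resident who gets back into bed unaided, and such falls may add few visits. This also stands, and may keep the problem small.

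Third, the wording is looser than it first looks. Design refers to detected falls and does not say detected by video; elsewhere the plan also speaks of falls detected by facilities and by staff. The Data collection sentence covers ER visits in controls only and is no evidence about hospitalisations. That ED capture follows the arm-specific fall route is an inference from the order of the sentences in Design, though the natural one.

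A reader might also infer that a visit with no known fall has a different chance of being counted in each arm. The documents do not support that. Under Design it is collected in neither arm, and under Clinical outcomes representatives are asked in both. The discrepancy there is between sections, not between arms.

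**Conclusion.** The point holds as an unreconciled conflict between Design, Data collection and Clinical outcomes. Following the first two permits differential ascertainment in the Hypothesis 3 comparison; following the third largely avoids it. The plan applies the relevant safeguard to Aim 1 and not to Aim 3, so this is more than a missing detail, and it should be settled.

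A reader might conclude that the Aim 3 events are certainly found by different routes and that the comparison is therefore biased. The documents show a risk of bias, not its presence. Nor is any distortion necessarily beyond repair: representatives' reports and released records are planned without arm distinction and would allow at least partial reconciliation.

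Direction and size are unknown. The range of 0.90 to 1.11 around a true ratio of 1.00 rests on assumed capture ratios of 0.9 and 1.11. The false-positive figures rest further on an assumed ED rate per fall, full follow-up, and a rate comparison. Data analysis instead describes a binary outcome and names no arm term.

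**What to change.** State in Clinical outcomes that one source, one contact schedule and one event definition govern the Aim 3 endpoint in both arms. A workable version uses the route already there:

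- Ask each participant's legal representative, at the same stated interval in both arms, about every ED visit and hospitalisation since the last contact, whether or not a fall was reported.
- Use released medical records under the same written rule in both arms, with the review done without knowledge of arm where feasible. This matters because representatives will know the allocation.
- Say whether the endpoint is any event, a count or days, and use that form in all sections.
- Do not use platform data, or case review triggered by detected falls, to find Aim 3 events. Keep both for Aim 2.
- Edit Design and Data collection to agree.

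Extending the full control-arm check to the intervention arm is not required. If biweekly means every two weeks, it would add about 13 × 230 = 2,990 resident-checks over six months.

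The cost is some added contact time with representatives. One round for all participants is 460 contacts before losses, so monthly contact would be 6 × 460 = 2,760. Events found only through case review would be lost from the count. Counting every visit also includes some that the system cannot influence, which pulls a true ratio towards 1. Marking fall-related visits by one rule in both arms would let that subset be reported alongside.

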#### Clinical outcomes.

For Aim #1, the primary outcomes are the number of falls detected by facilities using the adverse incident reporting system as per routine facility protocol. While use of video detected falls will be used in the intervention group to assist with prevention of future falls, we will not use this as the actual outcome measure: is not the standard-of-care, and the control group will not have video recorded outcomes. There is a bias for detecting falls using video since existing fall reporting systems do not capture falls which staff do not know about (e.g., when a resident is able to get back in bed after a fall). Staff-detected falls which automatically trigger adverse incident reporting is the “real-world” outcome measure and current stand-of-care. Thus, outcomes will differ by facility (each facility has different adverse incident reporting operations and implementation, hence the randomization at each facility will adjust for such variables).

Aim #2 will be a naturalistic observation of SafelyYou Guardian with HIL for 6 months. Specifically, for all the facilities, the use of the SafelyYou Guardian enables direct notification of falls to front-line staff in the facilities, by intervention of the HIL. We can directly measure time on the ground for the residents as follows: (1) The time of the fall is recorded by

SafelyYou Guardian (which detected it); (2) The time of intervention of the front-line staff is logged by the staff after finding the residents on the ground. This means that for the population with treatment, we can directly measure the time of fall discovery (successful call leading to front line staff intervention), and time on the ground (since time of the intervention is logged by the facility). This is because time on the ground for monitored residents can be measured precisely by video recording. Reduction of the time on the ground can be computed given the difference between the two.

Aim #3 will include number of ER visits and number of hospitalizations. We will obtain information about resident demographics, medical comorbidities, emergency room visits, and hospitalization data by asking the study participant legal representatives. In addition, we will have participant / participant Durable Power of Attorney complete HIPAA consent forms for release of medical records when indicated if the details of data are not available.

Data analysis: For aims 1, statistical analyses to address baseline comparison: Subjects' baseline characteristics (demographics and medical conditions) will be compared between the intervention and control groups using 2-sample t-tests (or appropriate nonparametric tests if the assumption of normality appears to be violated) and chi-square tests for continuous and categorical variables. Descriptive statistics will be used (means, frequencies, standard deviations, 95% confidence intervals) for all variables. We will examine the Aim #1a outcomes using a Poisson mixed-effects model to account for the nesting of outcomes within centers. We will account for baseline measures of resident activation and health status and resident demographics to statistically adjust for baseline imbalances, reduce residual intra-cluster correlation and improve the precision of estimated effects. Power analyses were performed via a simulation study in R version 3.4. and the lme4 package. We used 3 months of pilot data to guide and set assumptions for the data generating process. Based off initial data, we assumed centers ranged in size from 25-45 participants, and that roughly 30% of participants at each site would consent to the trial. Of those who consent, 50% will be randomized to the intervention. We fit the pilot data to a Poisson mixed effects model to obtain an estimate of the average monthly fall rate (0.49) as well as the between cluster variation in log fall rate ( $\sigma_{\text{twn}} = 0.467$ ). We generated 1000 sample data sets assuming different effect sizes (40%, 30%, 25% reduction in falls) and calculated the power obtained to detect this improvement due to intervention, as a function of the number of centers.

Following the sample size for a time-averaged response methodology laid out in Fitzmaurice et al., we adjusted the total number of centers needed by a factor related to the number of observed months, anticipated participants per center (30% of 35 participants per center with 10% dropout) and the correlation between measurement months. The dropout rate was roughly at ~1% per month so a 10% dropout over 6 months is a conservative estimate. We assumed an extremely conservative estimate of the correlation between time points (months) of 0.8 and 6 months of follow-up. Reproducible R code is available at <https://github.com/[name]/>. We estimate that a total sample size of 460 ( $n=230/\text{arm}$ ) out of 19 facilities will be needed for a power of 80% to detect a 30% reduction in falls in the intervention group vs. control. Our approach of focusing on estimation and uncertainty and accepting the sample size collected for the main study, is congruent with experts' recommendations stating that the purpose of economic evaluation is not hypothesis testing; given there is no hypothesis testing, there is no requirement for a separate sample size calculation. For Aim 2, we will use similar descriptive statistics as described in Aim 1. For Aim 3, We will use a multivariate regression model to examine predictors of the main outcome, ER visits and hospitalizations (binary variable), using time to fall discovery by staff and time spent on the ground as the main predictors while controlling for baseline participant characteristics and facility characteristics.

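### The alert call can change which falls staff know about and report, so Aim 1 fall detection may differ by arm, in an unknown direction, and the plan has no analysis for it

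*Combined protocol and SAP*

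**What the plan says.** All references are to the combined protocol and SAP.

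- **Outcome.** Clinical outcomes defines the Aim 1 outcome as falls that facilities pick up through their routine incident reporting, described as "Staff-detected falls which automatically trigger adverse incident reporting". It rules out video-detected falls as the outcome because "existing fall reporting systems do not capture falls which staff do not know about". Its example of a missed fall is "when a resident is able to get back in bed after a fall".
- **Safeguard.** The same section accepts that reporting practice varies between facilities, "hence the randomization at each facility will adjust for such variables".
- **Reporting duty.** Data collection notes that "State regulations require facility track and file incident reports for all known falls".
- **Intervention.** Under Design and Event Detection, a human in the loop (HIL) confirms that a resident is on the ground and contacts staff. Participant recruitment and retention says controls do not get this in the first 6 months.
- **Analysis.** The Data analysis text gives a Poisson mixed model with facility nesting and baseline covariates. It has no allowance for a detection difference, no split of reports by how staff learned of the fall, and no sensitivity analysis.
- **Other sources named.** The Aim 3 paragraph of Design describes case review of detected falls in the intervention arm and biweekly checks with staff and family for controls. Data collection says "data specific to the falls is collected either by direct extraction from the platform or from incident reports kept by facilities".

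**The concern.** Choosing incident reports over video keeps video detections from being counted directly. It does not stop them from being counted indirectly. A fall that staff learn of from the call is a known fall, and known falls are reported. Controls have no matching route, so the measuring process depends on treatment.

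Stratifying by facility equalises reporting habits between facilities. It cannot equalise two arms of the same facility when the treatment itself alters what staff know. Baseline covariates cannot do so either, because the difference arises after randomisation.

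Hypothesis 1 concerns fall rates, and reported falls stand in for them. If the share of falls reported differs by arm, the estimated rate ratio mixes the effect on falling with the effect on reporting. The plan as written could not separate a null result from a masked reduction, or a reduction in falls from a reduction in reports.

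**Working it through.** **1. Inputs from the Data analysis text.** Monthly fall rate 0.49; between-facility variation in log rate 0.467 (read as a standard deviation); 30% reduction (rate ratio 0.70); 230 per arm; 6 months; between-month correlation 0.8; power 80%. Not stated and assumed here: two-sided 5% level. Not stated anywhere: the share of falls that staff miss in either arm.

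**2. Reproducing the plan's figure.** The plan used simulation; this is a Wald approximation to it.
- Facility-averaged rate L = 0.49 × exp(0.467²/2) = 0.546 per month (derived, not stated in the plan).
- Correlation factor f = (1 + 5 × 0.8)/6 = 0.833.
- SE(log RR) = √[f/230 × (1/L + 1/(L × RR))] = 0.127 at RR = 0.70.
- Power = Φ(|ln 0.70|/0.127 − 1.96) = Φ(2.81 − 1.96) = 80.3%, against the stated 80%. This is without dropout.

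**3. Effect of unequal detection.** Let D be the share of falls reported in the intervention arm divided by the share reported in control. Then observed RR = true RR × D. This step does not depend on the power model. The values of D are assumptions.

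| D | Observed RR if true RR is 0.70 | True RR behind an observed 0.70 (0.70/D) |
|---|---|---|
| 0.90 | 0.63 | 0.778 |
| 0.95 | 0.665 | 0.737 |
| 1.05 | 0.735 | 0.667 |
| 1.10 | 0.77 | 0.636 |
| 1.20 | 0.84 | 0.583 |

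A true 0.70 would be hidden completely at D = 1/0.70 = 1.43.

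**4. What could put D above 1.** If u is the share of falls unknown to staff under usual care and c the share of those that the call makes known, D = (1 − u + u × c)/(1 − u). With u = 10%, D is 1.02 at c = 0.2 and 1.11 at c = 1. With u = 20%, it is 1.05 at c = 0.2 and 1.125 at c = 0.5. The documents give neither u nor c.

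**5. What could put D below 1.** Purpose says that seeing how a resident reached the floor shows when the move was intentional. Staff finding a control resident on the floor have no video to tell them so. If such events are then not reported as falls in the intervention arm, D falls. Whether this happens is not stated.

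**6. Illustrative consequences, same formula, correlation 0.8.**
- True RR 0.70: power is about 69% at D = 1.05 and 56% at D = 1.10. At correlation 0.3 the figures are about 94% and 85%.
- True RR 1.0 and D = 0.90: SE = 0.118 and |ln 0.90|/0.118 = 0.89. The chance of a significant apparent reduction is Φ(0.89 − 1.96), about 14%, against a nominal 2.5%.

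**The case against.** The best defence is that the plan saw the detection problem, chose the routine outcome deliberately, and uses one reporting system for both arms. The route may also be narrow. The plan's only example of a missed fall is a resident who is already back in bed, whereas the call follows confirmation that someone is on the ground. The plan does not say whether a call is made once the resident is up. A resident who stays on the floor may well be found in either arm. There are no cameras in bathrooms, where 5–10% of Phase I falls occurred, so c = 1 would need every missed fall to be on camera. All of this stands as a limit on size. None of it shows that D equals 1.

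The power figures are also weak evidence. They come from a formula fitted to the stated 80% without dropout. With the stated rate of 0.49 and 10% dropout (207 per arm), the same formula gives 71% at D = 1. The plan calls its correlation extremely conservative, and the pilots reported a 38% reduction, larger than the 30% used for sample size.

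A reader might infer three stronger things that the documents do not support:
- **That the bias must run against the product, so a positive result is conservative.** The intentional-floor-event route runs the other way, and nothing in the documents ranks the two.
- **That extra falls can enter the intervention arm only.** Residents are randomised individually, and Risk/Benefit Assessment requires all roommates to consent before any can take part. A control sharing a camera room could therefore also be detected.
- **That Aim 1 will count video falls in one arm and reports in the other.** Clinical outcomes rules this out. The Design text on case review is written for Aim 3, and the Data collection sentence is ambiguous. These need reconciling but do not show a planned mismatch.

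**Conclusion.** The concern holds as a treatment-dependent detection difference of unknown direction and size. The route follows from the plan's own statements: the outcome depends on staff knowledge, the intervention changes staff knowledge, and known falls are reported. Neither the within-facility randomisation nor the Poisson model corrects it. An assumed 10% difference in relative detection moves a true 0.70 to 0.63 or 0.77, so neither a null nor a positive Aim 1 result can be read at face value as an effect on falling.

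The relation between observed and true rate ratio is exact given D. Every value of D is an assumption, and the power figures are illustrative only. The finding does not show that the trial is underpowered or that the outcome should be replaced. It supports a cheap improvement to the analysis plan.

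**What to change.** 1. **One source.** Keep the Aim 1 outcome, each facility's routine reporting definition and the primary model. State in the Aim 3 paragraph of Design and in Data collection that the Aim 1 count in both arms comes only from facility incident reports.
2. **Flag first notice.** Mark each intervention-arm report for which the HIL call was staff's first notice. The plan already records "the time it took the HIL to verify the fall and call the facility", and says "The time of intervention of the front-line staff is logged by the staff after finding the residents on the ground". Check first that reports can be matched to these times by event, since the documents do not say so.
3. **Sensitivity analysis, fixed before any comparison by arm.** Report:
   - the rate ratio with all reports;
   - the rate ratio divided by assumed D on both sides of 1 (for example 0.90, 0.95, 1.05, 1.10, 1.20), with the D at which the conclusion changes;
   - the rate ratio without HIL-first reports, labelled an extreme bound, because staff would have found some of these falls anyway.
4. **Supporting evidence.** Compare falls with injury only if incident reports in both arms already record injury, which the documents do not say. Note that faster discovery may itself change recorded injury.

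The cost is SAP wording and record linkage. The bounds may be wide. If h is the HIL-first share of intervention-arm reports, excluding them multiplies the rate ratio by (1 − h), so an observed 0.77 becomes 0.69, 0.54 or 0.39 at h = 10%, 30% or 50% (assumed shares). The bias is bounded under assumptions, not removed, and possible under-reporting of intentional floor events remains a stated limitation.
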